1.0 Introduction

Lung cancer is the leading cause of worldwide cancer mortality, and is responsible for more deaths annually in the United States than the combination of breast, colorectal, and prostate cancer, with an estimated 1.04 million new cases each year worldwide (1-4). Non-small cell lung cancer (NSCLC) accounts for approximately 75% of all lung cancers, and of these approximately one third will develop brain metastasis at some time during the course of their disease. Additionally, 50% of all brain metastases are from lung primary tumors (5-7). Unfortunately, for the vast majority of these patients this diagnosis is associated with significant impairment and morbidity and drastically shortened survival. Present treatments for brain metastases include Surgery, Whole Brain Radiation Therapy (WBRT) and Stereotactic Radiosurgery (SRS). These modalities are often quite effective in alleviating symptoms; however, median survival remains poor, at around 2-7 months, (8) clearly new treatments are greatly needed.

1.1 Rationale:

The process of cell division, growth, differentiation and death is a highly regulated process. Several classes of trans-membrane receptors play a pivotal role in this process. Of these, epidermal growth factor receptor (EGFR) a member of Receptor Tyrosine Kinase (RTK) family is best known. This family is comprised of four receptors Erb B1/HER 1, Erb B2 / HER 2, Erb B3/ HER 3, and Erb B4 / HER 4. Activation of these receptors typically occurs via specific ligand binding, resulting in the hetero- or homodimerization between receptor family members, with subsequent autophosphorylation of the tyrosine kinase domain. This activation triggers a cascade of intracellular signaling pathways involved in both cellular proliferation (ras/raf/MAP kinase pathway) and survival (PI3kinase/AKT pathway).

Aberrant signaling through the epidermal growth factor receptor (EGFR) is associated with neoplastic cell proliferation, migration, stromal invasion, resistance to apoptosis, angiogenesis and metastatic spread (9). The critical role that EGFR plays in cancer has led to an extensive search for selective inhibitors of the EGFR signaling pathway. The results of a large body of preclinical studies and the early clinical trials thus far conducted suggest that targeting the EGFR could represent a significant contribution to cancer therapy. Furthermore, continuous stimulation of the EGFR-mediates signal transduction pathway may not only confer a growth advantage to malignant cells, but also a survival advantage following a genotoxic insult such as ionizing radiation (anti-apoptotic effects) (10).

Efficacy of this approach has been demonstrated in breast cancer with the blocking of the HER-2 receptor with the monoclonal antibody Herceptin. An alternate strategy is to inhibit EGFR TK activity using small molecules, like OSI-774 (Erlotinib, Tarceva™; OSI Pharmaceuticals) or ZD 1839 (gefitinib, Iressa™; Astra Zeneca) approved for use in lung cancer. Tarceva acts by reversibly inhibiting EGFR-TK thus inhibiting autophosphorylation of EGFR. Initial trials of daily oral Tarceva 150 mg QD (Study 248-1007) enrolled 56 patients with diagnosis NSCLC showed a 14.3% objective response rate and a 28.6% rate of disease stabilization. Tarceva was well tolerated and demonstrated predictable pharmacokinetics. Additionally, Tarceva was assessed in a Phase III, randomized, double-blind, placebo-controlled trial in 731 patients with locally advanced or metastatic NSCLC after failure of at least one chemotherapy regimen. In a 2:1 randomization (Tarceva: Placebo), patients received Tarceva 150 mg or placebo orally once daily until disease progression or unacceptable toxicity. The primary study endpoint was survival with additional endpoints of response rate and progression free survival. The results of the study indicated a statistically significant improvement in survival for Tarceva treated patients (6.7 mo vs 4.7 mo). Both secondary endpoints (PFS and Response) also favored the Tarceva arm with p value <0.001 (11).

Given that Tyrosine Kinase Inhibitors (TKIs) have been shown to have efficacy in patients with Non-Small Cell Lung Cancer (NSCLC), one would postulate that metastases from NSCLC primaries would also likely respond. NSCLC has a propensity to metastasize to the Central Nervous System (CNS). One of the greatest barriers in treating CNS malignancies lies in the limited drug penetration through the blood brain barrier (making therapeutics such as mAB's essentially useless in the brain). However, Heimberger et al, at Duke has shown that small molecule TKIs (ZD1839) not only cross the BBB but produce a 105% increase in survival in animal models with brain tumors compared to untreated controls (12). Furthermore, work published in our lab has demonstrated that the use of TKIs in vitro had a significant radiosensitizing effect and increased cell death when combined with external beam radiation (13). Furthermore, this synergistic effect of combining tyrosine kinase inhibitors and external beam radiation have been suggested by Bonner et al, work in head and neck cancer, that was recently presented in the Journal of Clinical Oncology (14). Lastly, the safety of combining Tarceva and external beam radiation in treating Central Nervous System (CNS) tumors has been recently demonstrated in a phase I study (15). In this dose escalation study with 20 patients with glioblastoma multiforme, Tarceva was dose escalated up to 200 mg per day, concurrently with external beam radiation of 60 Gy. Of the twenty patients, only one experienced a dose limiting toxicity of stomatitis. Given that we will be using a lower dose of both Tarceva and radiation (150 mg and 30 Gy respectively), we feel that this is a safe regimen.

Based on these observations, we hypothesized that the synergistic properties of TKIs along with external beam radiation may prove to be a well tolerated and efficacious means of extending overall survival and decreasing morbidity in patients with brain metastasis from NSCLC.

2.0 Study Objectives

2.1 Primary Endpoints:

To determine if Tarceva, given orally on a daily basis along with concurrent whole brain radiation therapy **improves median survival** of patients with brain metastases, compared with historical controls.

[figure not shown]
2.2 Secondary Endpoints:

- 2.2.1 To see if Tarceva along with concurrent WBRT, improves **quality of life** as assessed with the Spitzer Quality of Life Index (Appendix E) and the Folstein Mini-Mental Status Exam (Appendix F). Optional test will include Digit Span, Digit Symbol, Hopkins Verbal Learning Test, Controlled Oral Word Association, Trail Making Test Part A, Trail Making Test Part B, Grooved Pegboard, Barthel [name]. Anderson Symptom Inventory, and Functional Assessment of Cancer Therapy with Brain Module. As of July 18, 2012- Optional tests will no longer be completed.
- 2.2.2 To see if Tarceva along with concurrent WBRT, influences cause of death compared to matched controls, based on key attributes such as stage, age KPS, number of brain metastasis, etc.
- 2.2.3 To see if Tarceva along with concurrent WBRT, increases time to progression of disease.
- 2.2.4 To sequence the EGFR receptor of patients treated with Tarceva, in order to identify specific gene mutations that may correlate with favorable responses to Tarceva.
- 2.2.5 To study downstream proteins involved in the EGFR cascade such as p-EGFR, Raf, PKC, JNK, and p-AKT. This information will be combined with other protein markers such as E cadherin that appear to increase the probability of response, in the hopes of developing a genetic signature of patients most likely to benefit from this regimen.
- 2.2.6 To confirm the safety profile of Tarceva along with concurrent external beam radiation therapy, in the context of treating central nervous system malignancies.
- 2.2.7 To provide evidence to support a much larger multi-institutional study.

3.0 Study Design

Twenty patients will be collected from this M.D. Anderson based study and the data will be combined with an identical 20 patient study that [name] started while at the Arizona Cancer Center. The Arizona study has enrolled 15 of the planned 20 patients (as of August 2008), and by combining these two studies we will have a total of 40 patients for final analysis.

Study Schema

Patients must have radiographic evidence of brain metastases, proven with CT or MRI so that we can stratify patients by the number of brain metastases. Additionally, they must have no prior history of cranial radiation (other than stereotactic radiosurgery). Once enrolled, patients will receive Tarceva (150mg PO QD) for at least 6 days prior to starting and during whole brain radiotherapy (WBRT). External beam radiation will consist of opposed laterals to a total dose of 3500cGy in 14 daily fractions.

Upon completion of external whole brain radiation, patients will continue taking Tarceva (150mg PO QD) until documentation of disease progression (unless treating physician feels that stopping Tarceva would adversely affect the patient) or if patients are unable to tolerate study drug due to toxicities. Patients will be allowed to stop taking Tarceva at any time during this trial. Following completion of WBRT patients will have a repeat MRI or CT at 1 month after completion of WBRT, and then at 3 month intervals, or sooner if indicated by symptom progression. Additionally, during active treatment period of this trial, patients will not be allowed to have surgical debulking of CNS tumors, or stereotactic radiosurgery of CNS lesions, as this need would correlate with progression of disease. Patients will be allowed to receive palliative radiation if needed to address symptoms. Patients will be allowed to dose reduce down to 50mg per day, and may also take a treatment break of up to seven days.

Survival will be compared to a database of patients with similar histologies and stratified according to their Recursive Partitioning Analysis (RPA) class and the number of brain metastases, at time of diagnosis (16). The RPA is a predictive tool used to estimate survival based on age, performance status, and presence of extracranial metastasis.

The vast majority of patient will either be and RPA class I or II, which predicts for a survival of 7.1 and 4.2 months respectively. Patients that elect for tumor protein expression analysis will go on to have their tumors tested for EGFR expression along with receptor sequencing, if possible. This will serve to identify if specific gene mutations may correlate with favorable responses to Tarceva. Additionally, we will also study proteins thought to predict anti-EGFR response such as Vimentin, E-Cadherin, Fibronectin, PTEN, PKC, c-Met and p-AKT. This information will be use to determine if a genetic signature of patients most likely to benefit from this regimen can be identified.

4.0 Eligibility Criteria

4.1 Inclusion Criteria

- 4.1.1 Histological confirmation of non-small cell lung cancer
- 4.1.2 Patients who have been treated in the past with Stereotatic radiosurgery, Stereotactic Radiotherapy, GliaSite or surgical resection will be allowed to enroll in this study
- 4.1.3 A diagnostic contrast-enhanced MRI or CT scan must be performed, demonstrating brain metastases
- 4.1.4 Age 18-70
- 4.1.5 Patients must have KPS \geq 70
- 4.1.6 Patients cannot be treated on any other treatment related clinical protocols within 30 days prior to study entry or during participation in the study
- 4.1.7 No uncontrolled or symptomatic major medical illnesses or psychiatric impairments, such as Alzheimer's or schizophrenia
- 4.1.8 Screening Clinical Laboratory Values: ANC >1500/ul, Platelets >80,000/ul, baseline AST and/or ALT within normal limits (within 30 days of starting protocol treatment).
- 4.1.9 All women of childbearing potential (A woman of child-bearing potential is a sexually mature woman who has not undergone a hysterectomy or who has not been naturally postmenopausal for at least 24 consecutive months [i.e., who has had menses at any time in the preceding 24 consecutive months]) and male participants must practice effective contraception (abstinence, oral, injectable, or implantable hormonal contraceptive; tubal ligation; intra-uterine device; barrier contraceptive with spermicide; or vasectomized partner) throughout the study. All women of child-bearing potential must have a negative serum pregnancy test and practice birth control while on study.
- 4.1.10 Patients must provide verbal and written informed consent to participate in the study

4.2 Exclusion Criteria

- 4.2.1 Prior cranial radiation therapy, other than stereotatic radiosurgery, Stereotactic Radiotherapy or GliaSite.
- 4.2.2 Patients with known Acquired Immune Deficiency (*AIDS*), as regimens with tyrosine kinase inhibitors may pose a safety risk related to excess toxicity or interference with anti-viral effectiveness
- 4.2.3 Women who are pregnant or lactating, due to possible adverse effects on the developing fetus or infant due to study drug
- 4.2.4 Patients with active connective tissue disorders, such as lupus or scleroderma

5.0 Study Medications

5.1 Description

Tarceva (Erlotinib Hydrochloride):

Tarceva is a quinazolinamine with the chemical name N-(3-ethynylphenyl)6,7 bis(2methoxyethoxy)-4-quiniazolinamine and contains Erlotinib 2 Clinical Formulations. In addition to the active ingredient, Tarceva tablets contain lactose (hydrous), microcrystalline cellulose, sodium starch glycolate, sodium lauryl sulfate, and magnesium sulfate. The molecular weight of Tarceva (Erlotinib) is 429.90. It is slightly soluble in water, slightly soluble in methanol and practically insoluble in acetonitrile, acetone, ethyl acetate and hexane.

5.2 Pharmacology

The mechanism of clinical antitumor activity of Tarceva is not fully characterized. Tarceva inhibits the intracellular phosphorylation of tyrosine kinase associated with the epidermal growth factor receptor (EGFR).

Bioavailability of Tarceva following a 150mg oral dose is about 60% and peak plasma levels occur 4 hours after dosing. Food increases bioavailability substantially to almost 100%. Tarceva's half life is about 36 hours and it is cleared predominantly by CYP3A4 metabolism. Time to reach steady state plasma concentration is 7-8 days and no significant relationship has been observed of clearance to patient's age, body weight or gender. Smokers have a higher rate of Tarceva clearance than non-smokers. Tarceva is predominantly cleared by the liver. No data are currently available regarding the influence of hepatic dysfunction or hepatic metastases on the pharmacokinetics of Tarceva. Since Tarceva is predominantly metabolized by CYP3A4, inhibitors or inducers of CYP3A4 would be expected to increase and decrease exposure, respectively. A potential for drug-drug interaction exists when Tarceva is co-

administered with drugs that are highly protein bound or that are CYP3A4 and CYP1A2 inhibitors/inducers.

For patients who are being concomitantly treated with a potent CYP3A4 inhibitor, a dose reduction should be considered in the presence of severe adverse events. For patients who are being concomitantly treated with a potent CYP3A4 inducer, alternative treatments that lack potent CYP3A4-inducing properties should be considered.

Patients taking an enzyme-inducing anti-convulsant medication (phenytoin, carbamazepine, phenobarbital, Mysoline, Trileptal). It should be discontinued and converted to a nonenzyme-inducing anti-convulsant (Keppra, Depakote, Topamax, Lamictal or Neurontin) prior to the first dose of Tarceva.

In addition, altered coagulation parameters and bleeding have been reported in patients receiving Tarceva alone and in combination with other chemotherapeutic agents and concomitant warfarin-derivative anticoagulants. The mechanism for these alterations is still unknown. When warfarin is coadministered with Tarceva (anytime after Day 5), international normalized ratio (INR) and prothrombin time should be closely monitored (weekly until stabilized) and the anticoagulant dose should be adjusted as clinically indicated.

5.3 Adverse Events/Precautions

The most common adverse reactions in patients receiving Tarceva monotherapy and in combination with chemotherapy are rash and diarrhea. Grade 3-4 rash and diarrhea occurred in 9% and 6%, respectively in Tarceva treated patients. Rash and diarrhea each resulted in study discontinuation in 1% of Tarceva treated patients. The median time to the onset of rash was 8 days and the median time to onset of diarrhea was 12 days.

There have been infrequent reports of ILD (interstitial lung disease) in patients receiving Tarceva for the treatment of NSCLC and other advanced solid tumors. In the randomized single agent study, the incidence of ILD (0.8%) was the same for both the placebo and Tarceva groups. The overall incidence of ILD from all studies was approximately 0.6%. If ILD is diagnosed, Tarceva should be discontinued and appropriate treatment instituted as necessary. There are no adequate and well controlled studies of Tarceva in pregnant women. Women of childbearing potential should be advised to avoid pregnancy while on Tarceva, and will need to practice birth control while on study, if premenopausal.

Asymptomatic increases in liver transaminases have been observed in patients on Tarceva; therefore, periodic liver function testing should be considered. Also, patients taking warfarin or other coumarin-derivative anti-coagulants should be monitored for

changes in prothrombin time or INR. NCI-CTC grade 3 conjunctivitis and keratitis have been reported infrequently in patients receiving Tarceva therapy. Corneal ulcerations may also occur.

5.4 Packaging, Supply, and Labeling

Tarceva (Erlotinib) will be supplied by OSI at no cost for each study patient. The pharmaceutical preparations of Tarceva are formulations containing the hydrochloride salt (OSI 774 01). Tarceva is supplied as tablets containing erlotinib hydrochloride equivalent to 150 mg, 100 mg, and 25 mg of erlotinib. All tablets are round, white, film-coated, bi-convex tablets without markings. Each bottle will be labeled with the drug name, pill dose, number of pills, manufacture date, Lot # and expiration date.

5.5 Storage

Tarceva tablets should be stored between 15°C and 30°C (59°F and 86°F).

5.6 Administration

Patients will receive only a 30-day supply of drug at a time, from the Investigational Pharmacy. The patient will be seen by the nurse once approximately every 30 days (+/- 7 days) to review number of pills taken during the previous 30 days (+/- 7 days), and to receive another 30 days of medication. If patients are unable to return for their follow up visits, we will review their mediations and current drug logs over the phone and their Tarceva refills will be mailed to them via the investigational pharmacy.

Patients will begin taking Tarceva at least 6 days before their first dose of radiation, daily during radiation therapy, and then daily until progression is documented (unless treating physician feels that stopping Tarceva would adversely affect the patient), adverse events warrant discontinuation or the patient decides to stop taking the medication.

Tarceva tablets should be taken once daily. Each Tarceva dose is to be taken with up to 200 mL (~ 1 cup or 8 oz) of water, and should be taken 1 hour before or 2 hours after meals or medications, including grapefruit juice, vitamins, and iron supplements.

For patients residing outside the U.S: Patients will receive a 90 day supply of Tarceva at a time, from the Investigational Pharmacy; The study PI will have physician-to-physician communication regarding protocol enrollment; a letter (Appendix G) will be sent to the home physician outlining the subject's participation and requesting the home physician agreement to supervise the subjects care. The home physician will be requested to provide any patient medication diaries, progress notes, hospitalization records, toxicities, tests, and procedures to the study PI or his research staff at MD Anderson within 48 hours. The home physician will be asked that any questions related to the study drug dosing, schedule, or side effects be directed to study PI. All life

threatening clinical events must be reported by the home physician to the study PI within 24 hours of documented occurrence. The home physician will be provided with study contact numbers for business and non-business hours.

Protocol required evaluations outside MDACC will be documented by telephone, fax or e-mail. Fax and/or e-mail will be dated and signed by the MDACC physician, indicating that they have reviewed it.

Changes in drug dose and/or schedule must be discussed with and approved by the MDACC physician investigator, or their representative prior to initiation, and will be documented in the patient record.

A copy of the informed consent, protocol abstract, treatment schema and evaluation during treatment will be provided to the local physician.

Patients will return to MDACC every 3 months for evaluation.

5.7 Accountability

In accordance with current Good Clinical Practices (GCPs), the investigational site will account for all supplies of Tarceva. Details of receipt, storage, administration, and return or destruction will be recorded in the study drug accountability record according to the standard operating procedure of the investigational site. The drug will be delivered to and distributed by the investigational pharmacy of MD Anderson for clinical investigations.

All unused supplies of Tarceva (from the study and unused drug from patients) will be destroyed after completion of the trial, as per pharmacy SOPs. Copies of the study drug accountability record will be provided to OSI Pharmaceuticals. Patients unused drug will be returned to the research nurse.

6.0 Study Methods

Study Calendar

Assessment	Screening	Baseline (1-3 days prior to day 1 of Tarceva)	Weekly During treatment	One Month Post RT (+/- 7 days)	Follow-up for patients on Tarceva (+/- 7 days)	Follow-up for patients off Tarceva (+/- 14 days)^{m,n,o}
-------------------	------------------	--	--	---	---	---

Histological confirmation of NSCLC	X					
CT/MRI of brain and report	X^b			X	X^m	X
CBC/Differential	X^b					
Platelet	X^b					
Complete Metabolic panel)	X^b					
Repeat sodium level			X^e			
CT or PET of Liver	X^c					
Medical History	X	X^d			X^{d,f}	X^d
Physical Examination	X^b		X	X	X^m	X
Concomitant Medications	X	X	X	X	X^{a,f}	
Serum Pregnancy test, if applicable	Xⁱ					

Assessment	Screening	Baseline (1-3 days prior to day 1 of Tarceva)	Weekly During treatment	One Month Post RT (+/- 7 days)	Follow-up for patients on Tarceva (+/- 7 days)	Follow-up for patients off Tarceva (+/- 14 days)^{m,n,o}
Document steroid dose		X	X	X		
Spitzer Quality of Life Index		X^k	X^l			
Folstein Mini-Mental Status Exam		X^k	X^l			
Optional neurocognitive tests ^p		X^k				
Consent for EGFR expression testing (Optional)	X					
Informed Consent	X					
Vital Signs		X		X	X^m	X
Adverse Event Check ^g			X	X	X^f	X
PT/INR if patient on Coumadin	X		X^{h,j}	X^h	X^h	X

a = until 30 days after last dose of Tarceva

b = within 30 days of starting treatment

c = within 3 months of starting treatment

d = update only

e = Patient will have repeat sodium on RT day 7 and RT day 14 if baseline sodium \leq 135 mg/dl

f= Patients will be seen by the research nurse monthly while on Tarceva (+/- 7 days), and/or one month post last dose of Tarceva (+/- 7 days). Patients on Tarceva, who are unable to return for their follow up visits and 1 month post last dose of Tarceva visit, will be contacted by the research nurse by phone to review/asses the following; Update of medical history, assessment of AE's concurrent medications. They will return their unused Tarceva medication along with their medication diaries to the research nurse via mail.

- g= All adverse events will be collected until 30 days after the last study dose of Tarceva or 30 days post RT visit (whichever is last), then only neurocognitive decline will be captured.
- h = Only if patient has abnormal values during initial screening testing
- i= within 7 days of starting protocol treatment
- j= weekly until stable
- k= Prior to radiation
- l = During last week of radiation therapy (+/- 7 days)
- m= every 3 months (+/- 14 days) for 2 years then every 6 months after
- n= patients with deteriorating conditions who are unable to return may be followed up by telephone. MRI brain, physical exam, mini-mental exam, QOL Index and neurocognitive testing may be excluded.
- o= for patients with progressive CNS disease we will record survival only.
- p= Optional neurocognitive tests will include Digit Span, Digit Symbol, Hopkins Verbal Learning Test, Controlled Oral Word Association, Trail Making Test Part A, Trail Making Test Part B, Grooved Pegboard, Barthel [name]. Anderson Symptom Inventory, and Functional Assessment of Cancer Therapy with Brain Module. As of July 18, 2012- Optional tests will no longer be completed.

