7.0 Radiation Therapy

Radiation therapy will be given once per day, five days a week for 14 days. Radiation will be given at a dose of 250 cGy per day for 14 fractions for a total dose of 3500 cGy. Radiation will be delivered with 6MV photons using opposed lateral beams dosed to mid plane.

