8.0 Adverse Events

All adverse events will be graded according to NCI CTC version 3.0

Adverse drug experience means any adverse event associated with the use of a drug in humans, whether or not considered drug related, including the following: an adverse event occurring in the course of the use of a drug product in professional practice; an adverse event occurring from drug overdose, whether accidental or intentional; an adverse event occurring from drug abuse; an adverse event occurring from drug withdrawal; and any failure of expected pharmacological action (21 CFR 314.80).

An adverse event is any adverse change from the subject's baseline condition, including any clinically significant laboratory test value abnormality that occurs during the course of the clinical study after the informed consent is signed, whether the adverse event is considered related to the treatment or not.

All adverse events will be collected until one month post last day of Tarceva or radiation (whichever is last). This may require obtaining clinical blood samples for appropriate laboratory tests until their values return to baseline levels or performing follow-up physical examinations until resolution of identified abnormalities.

The most common adverse reactions in patients receiving single-agent TARCEVA 150 mg were rash and diarrhea. Grade 3/4 rash and diarrhea occurred in 9% and 6%, respectively, in TARCEVA-treated patients. Rash and diarrhea each resulted in study discontinuation in 1% of TARCEVA-treated patients. Six percent and 1% of patients needed dose reduction for rash and diarrhea, respectively. The median time to onset of rash was 8 days, and the median time to onset of diarrhea was 12 days.

	TARCEVA 150 mg N = 485			Placebo N = 242		
NCI CTC Grade	Any Grade	Grade 3	Grade 4	Any Grade	Grade 3	Grade 4
MedDRA Preferred Term	%	%	%	%	%	%
Rash	75	8	<1	17	0	0
Diarrhea	54	6	<1	18	<1	0
Anorexia	52	8	1	38	5	<1
Fatigue	52	14	4	45	16	4
Dyspnea	41	17	11	35	15	11
Cough	33	4	0	29	2	0
Nausea	33	3	0	24	2	0
Infection	24	4	0	15	2	0
Vomiting	23	2	<1	19	2	0
Stomatitis	17	<1	0	3	0	0
Pruritus	13	<1	0	5	0	0
Dry skin	12	0	0	4	0	0
Conjunctivitis	12	<1	0	2	<1	0
Keratoconjunctivitis sicca	12	0	0	3	0	0
Abdominal pain	11	2	<1	7	1	<1

Rare, But Serious

In some patients taking erlotinib and oral blood thinners INR have been reported abnormally elevated. The elevation of INR was associated with bleeding.

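### Study calendar footnote e gives the repeat-sodium threshold in the wrong unit: 135 mg/dl is 58.7 mmol/L, and 135 mEq/L was evidently meant

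*Combined protocol and SAP*

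**What the plan says.** The study calendar in section 6.0 has a row headed "Repeat sodium level". As the table reads, its only entry is in the column for weekly assessments during treatment, and that entry carries footnote e: "Patient will have repeat sodium on RT day 7 and RT day 14 if baseline sodium \leq 135 mg/dl".

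The same calendar lists "Complete Metabolic panel" at screening only, within 30 days of starting treatment. That panel is presumably where the baseline sodium comes from. The two repeat days refer to the radiation course in section 7.0: "Radiation will be given at a dose of 250 cGy per day for 14 fractions for a total dose of 3500 cGy".

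**The concern.** The footnote is a decision rule: a number and a unit determine who has two further blood draws. The number 135 is plausible for serum sodium in mEq/L and implausible in mg/dl. If the unit is taken at face value, the rule selects nobody, and the repeat-sodium row becomes an entry that never applies.

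What is at stake is modest. The conditional repeat is the only sodium measurement that the calendar schedules during treatment, so the footnote is the sole source for who should have it. Staff applying the rule, and anyone later checking adherence to it, need the printed threshold to be the intended one. Nothing in section 11 depends on it.

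**Working it through.** The plan gives no derivation of the threshold, so there is no calculation of its own to reproduce. The check is a unit conversion followed by a search for any text that would override the footnote.

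**Inputs**
- Threshold: 135, in mg/dl (section 6.0, footnote e).
- Molar mass of sodium: 22.99 g/mol, that is 22.99 mg per mmol. This is a physical constant and is not in the documents.
- Sodium carries one charge, so 1 mmol/L = 1 mEq/L.

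**Step 1: the printed limit in mmol/L**

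mmol/L = (mg/dl × 10) / 22.99

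135 × 10 / 22.99 = 1350 / 22.99 = 58.7 mmol/L

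**Step 2: the evident limit in mg/dl**

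mg/dl = mmol/L × 22.99 / 10

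135 × 22.99 / 10 = 310.4 mg/dl

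Ratio of evident to printed limit: 310.4 / 135 = 2.30.

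**Step 3: would the printed rule select anyone?** The sodium values below are illustrative assumptions, since the documents give no sodium data.

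| Sodium (mmol/L = mEq/L) | Sodium (mg/dl) | At or below 135 mg/dl? | At or below 135 mEq/L? |
|---|---|---|---|
| 100 | 229.9 | no | yes |
| 110 | 252.9 | no | yes |
| 120 | 275.9 | no | yes |
| 130 | 298.9 | no | yes |
| 135 | 310.4 | no | yes |
| 145 | 333.4 | no | no |

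Under the printed unit no row qualifies. Under mEq/L the rule separates low from normal values, which is what such a condition is for. Section 4.1.5 requires a KPS of at least 70, and a patient fit enough to enrol could not have a sodium of 58.7 mmol/L.

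**Step 4: does anything else correct the unit?**
- Section 4.1.8 sets screening limits for neutrophils, platelets and transaminases, and none for sodium.
- Section 6.4 (dose modification) and section 7.0 (radiation) do not mention sodium.
- Elsewhere sodium appears only in the names of tablet excipients (section 5.1).

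Footnote e therefore stands alone.

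**The case against.** The strongest reply is that nobody would be misled. A nurse or physician comparing the footnote with a laboratory report in mEq/L would see what 135 means and order the repeats. No clinician would act on a sodium limit of 58.7 mmol/L. On this view the factor of 2.30 measures a reading that no one would adopt, and the item is editorial.

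Most of that stands. A reader might infer from the literal arithmetic that the day 7 and day 14 samples would go undrawn. The documents do not support that as a prediction: they say nothing about how sites applied the footnote, and the number itself points to the intended unit.

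A reader might also infer that the rule is a safety trigger governing the radiation course. That too goes beyond the text. No purpose is stated for the repeat sodium, and no treatment hold, dose change or other action is tied to its result. Section 8.0 does count as an adverse event "any clinically significant laboratory test value abnormality that occurs during the course of the clinical study", but that is a general definition and makes no sodium-specific rule.

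What does not stand is the step from easily understood to correct. The footnote is current operative text, the unit is complete and legible, and followed as printed it gives the wrong answer for every low value in the table.

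**Conclusion.** Wrong as written, minor, with high confidence in the error itself. The printed threshold is 58.7 mmol/L where 135 mmol/L is evidently meant, a factor of 2.30 too low, and as printed it would not be met even in marked hyponatraemia.

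The conclusion rests on the molar mass of sodium and on the inference that 135 was chosen as a value in mEq/L. The first is not in doubt. The second is strongly supported, because only that unit gives a condition that an enrolled patient could meet. The practical effect is probably small, for the reason given in the objection, and the number of patients for whom it mattered cannot be derived from the documents. The point has no bearing on the primary endpoint, the sample size of 40 or the planned analyses.

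**What to change.** In footnote e of the study calendar, replace mg/dl with mEq/L (or mmol/L, which is numerically the same for sodium). Leave the number 135, the direction of the inequality and the two repeat days unchanged.

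The cost is one changed unit. It adds no visit and no test beyond those the footnote already intends, and it does not alter eligibility, treatment or analysis.
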